## Specific Aims/Objectives

Although pediatric professional guidelines are now recommending medical providers screen for social determinants of health (SDoH), there is no evidence to date that SDoH screening improves the health of pediatric patients and studies have fallen short of exploring its impact on the health of children with medical complexity, including children with sickle cell anemia (SCA). The proposed mixed-methods study aims to understand the implementation of a previously tested, efficacious SDOH screening and referral intervention in the outpatient pediatric hematology setting; qualitatively assess possible mechanisms for such interventions on improving child health; and obtain population-specific empirical estimates to plan a large-scale clinical trial.

Our specific aims are to: (1) Implement WE CARE in two pediatric hematology clinics in order to field test key study logistics and understand the facilitators and barriers to implementation and accelerate its adoption; (2) Obtain population-specific empirical estimates of study parameters to plan a large-scale multi-site cluster RCT of WE CARE that will definitely assess its impact on improving health outcomes for children with SCA; and (3) Qualitatively assess possible mechanisms linking social determinants of health interventions to improved health outcomes.

## Background and Significance

### **Social determinants of health are key drivers of health and health disparities, beginning in childhood.**

The social determinants of health (SDoH) – the social circumstances in which people are born, work, live, and age – affect disparities in risk and health outcomes through a myriad of physiological and behavioral pathways. Some have estimated that up to 70% of variation in health outcomes is attributable to SDoH. SDoH such as unmet material needs (e.g., food insecurity), has been linked to detrimental health and healthcare utilization outcomes, including higher rates of hospitalizations. The correlation between poverty and SDoH is well established, with those living in impoverished conditions more likely to have unmet material needs. Unfortunately, children constitute the poorest segment of the population in the United States (US) with racial/ethnic minority children disproportionately affected. Childhood is a particularly vulnerable period for the imprinting of harmful environmental exposures associated with poverty and its related adverse social determinants (e.g., food insecurity, housing instability, parental unemployment, and lack of high-quality childcare) and has been shown to affect health across the lifespan. *Children with medical complexity are especially at-risk and have been designated as a priority population for health care policy given their high healthcare need and utilization compared to healthy children.* Overall, approximately one in five children in the US has a medically complex condition.

### **The medical system is increasingly recommending routine SDoH screening at healthcare visits.**

Although addressing SDoH has long been a goal of the US public health system, it was not a key priority in the delivery of medical care until recently when the World Health Organization (WHO) and National Academy of Medicine (NAM) emphasized the need for clinicians and health systems to address SDoH within the context of healthcare visits. In 2016, the American Academy of Pediatrics (AAP) became the first medical organization to recommend screening for SDoH at pediatric visits, and listed [name] (study PI) WE CARE instrument as an example of an evidence-based screening tool. In addition, the Centers for Medicare & Medicaid Services invested \$157 million in their Accountable Health Communities initiative, which is implementing SDoH screening and referral in 32 sites across the US and assessing its impact on reducing unnecessary healthcare utilization, primarily in adults. Finally, some Medicaid programs, such as the one in Massachusetts, have developed value-based payment models that provide additional payments for patients identified as having unmet social needs, such as housing, thereby incentivizing SDoH screening.

**The Problem: There is no evidence that SDoH screening improves child health, and the underlying mechanisms for how SDoH screening may improve health remains unexamined.** Although there is strong epidemiological evidence linking adverse SDoH and detrimental health and healthcare utilization outcomes, *there is no evidence, to date, demonstrating the success of SDoH screening and referral interventions on improving child health.* Two recent studies offer promising preliminary results: one demonstrating increased parental report of excellent/very good child health in primarily healthy children; the other demonstrating improvement in blood pressure and cholesterol levels in adults.

In addition, *the underlying mechanisms by which SDoH screening and referral interventions can improve*

*child health are also currently unknown.* Understanding the processes linking SDoH interventions and health outcomes has the dual benefit of contributing to our scientific knowledge of SDoH and informing treatment targets in future intervention studies. Since SDoH burden falls disproportionately on those with lower socioeconomic status and on racial/ethnic minority families, it will be critical to examine these processes within diverse samples. Given the significance of this emerging field, the NIH is convening a workshop on SDoH screening and referral interventions and its future research directions in May 2018.

**Children with sickle cell anemia are the ideal population in which to study how SDoH interventions may improve health.** Sickle cell disease affects approximately 100,000 people in the US, primarily those of African and Hispanic descent. Sickle cell anemia (SCA) is the most severe form and represents approximately 60% of the sickle cell population. Manifestations of SCA, including sepsis and painful vaso-occlusive episodes, begin in infancy and expected survival is approximately 45 years, nearly 30 years less than for African Americans overall. Use of daily antibiotic prophylaxis in children with SCA until age 5 years reduces mortality, especially in early infancy. Guidelines also recommend that hydroxyurea (HU) be offered to children with SCA beginning at 9 months of age. *However, adherence to therapies proven effective for SCA is low.* One study of >2,800 eligible children with SCA found that only 18% had prescriptions filled for antibiotic prophylaxis for  $\geq 300$  days, far short of the recommended daily intake. In addition, a study of a state Medicaid program showed that only 41% of children prescribed HU were adherent, defined as supplied (from pharmacy records) to cover at least 80% of days in a year. A recent meta-analysis found mixed findings regarding the possible mechanisms underlying low rates of medication adherence among children with sickle cell disease, with medication barriers (e.g., competing demands) having the strongest effect size.

In addition to the high morbidity and low adherence, most children with SCA live in impoverished households. A multicenter clinical trial found that children with SCA live in households with a median income of \$6,250. Another study also demonstrated that over 90% of families of children with sickle cell disease have at least one unmet material need. Although not yet examined empirically, per *Maslow's Hierarchy of Needs model* (see C1) it is very likely that difficulties related to adverse SDoH, such as food or housing insecurity, likely impede parents' ability to adhere to treatment plans by limiting the degree to which parents can focus on SCA as opposed to more basic tasks of living. *In sum, SCA is an ideal medically complex condition in which to test the impact of an evidence-informed SDoH screening and referral intervention on improving child health outcomes due to its significant morbidity; most children with SCA live in impoverished households; and the known association between poverty and SDoH that likely impacts parental disease management.*

**Significance: Our proposal has significant potential to inform the burgeoning SDoH interventional research field, transform current clinical practice and improve health outcomes for medically complex children.** Although medical organizations and payers are increasingly recommending routine SDoH screening in medical practices, there is an absence of clinical trials on SDoH screening and referral interventions that assess health outcomes. This study addresses this clinically- and policy-relevant research gap by determining how to exert transformational practice change to implement an intervention that systematically addresses SDoH into the care for medically complex children (such as those with SCA), and exploring its impact on healthcare utilization and outcomes. Studies and practice guidelines for SCA, to date, primarily focus on pharmacologic interventions, as opposed to modifying social and environmental contributors to disease. While the contribution of social adversity and socioeconomic factors to the morbidity and mortality of SCA has been demonstrated, no one has yet developed an intervention that modifies these factors as a part of routine clinical care, nor have they carefully considered the processes through which SDoH impacts child health outcomes. Our mixed-

methods findings will inform whether, and how, to provide SDoH screening on a larger scale in the future. It will also add significantly to the sickle cell disease implementation science field since there is a great need for this type of research given the paucity of prior dissemination and implementation studies in children with SCA. More broadly, the knowledge gained from this proposal is likely to be directly translatable and applicable not only to SCA but also to other medically complex conditions. From a societal perspective, this proposal has great significance, as approximately one in five children in the US has a medically complex condition such as SCA, and these children are a priority population for healthcare policy given their high healthcare need and utilization. Given the near universal reach of child healthcare, this proposal has significant public health implications.

## Preliminary Studies

### **Family-centered approach for addressing SDoH for low-income children utilizing existing clinical infrastructure: the WE CARE Model.**

Our extensive groundwork has demonstrated that a family-

centered screening and referral intervention that relies on parental desire for assistance administered during pediatric preventive care visits led to increased provider referrals for, and parental receipt of, community resources. WE CARE (Well-Child care visit, Evaluation, Community Resources, Advocacy, Referral, Education) was efficacious in connecting families to community resources and resulted in

higher parental employment, receipt of fuel assistance and childcare, and lower odds of living in a homeless shelter, thereby reducing material need when tested in pediatric primary care clinics.

Ongoing work is providing a better understanding for the barriers (e.g., staff burden, lack of time and/or resources) and facilitators (e.g., clinic culture and leadership) for implementing this relatively simple intervention in general pediatric practice. This is necessary given the well-known challenge of incorporating efficacious innovations into routine medical practice. *Our WE CARE studies so far have focused on children without medically complex conditions and have been implemented only in primary care pediatric practices. Our studies to date have not been designed to measure the impact of WE CARE on child health outcomes, since they have targeted parents with healthy children.*

***Our team has conducted extensive groundwork to develop and implement a family-centered system for SDoH screening and referral in safety-net pediatric primary care clinics. We have crafted and validated a screening tool for six material needs and tested it among parents at general pediatric clinics. Given its reliance on existing clinical processes and infrastructure (i.e. no additional staff), we have purposefully measured implementation metrics in our recent studies. We have developed a system and feasible workflow (with documented acceptability for providers, staff, and parents) for administering the tool in the primary care setting. This work documented that use of the tool results in identification of unmet SDoH needs for which parents desire help, elicits referrals by the clinical team to community resources, and leads to actual receipt of services by parents. We have also developed simple, easy-to-use community resource sheets to address each type of social need.***

## Design and Methods

### *Study Design*

#### ***Study 1 (Aim 1): The implementation of a practice-based social determinants of health screening and referral intervention in two pediatric hematology clinics to field test key study logistics and understand the facilitators and barriers to implementation and accelerate its adoption***

Two of our four proposed pediatric hematology clinical sites will be randomized to implement WE CARE as standard of care for SCA patients. At baseline and every six months throughout the study period, the Boston Medical Center-based team (hereafter termed the core research team) will conduct focus

groups with stakeholders (e.g., clinical and administrative staff) at each of the four pediatric hematology clinic sites to better understand the barriers and facilitators to implementation of WE CARE. The site PI at each institution will help us identify staff members. Before beginning each focus group, the Boston Medical Center PIs and members of their research team will meet with clinic stakeholders at their staff meetings and provide an overview of the study. The Boston Medical Center-based team will conduct focus groups with pediatric hematology clinic staff every six months throughout the study period.

***Study 2 (Aim 2): Obtaining population-specific empirical estimates of study parameters to plan a future large-scale cluster RCT of WE CARE for children with SCA***

For this study, we will be conducting a pilot cluster RCT. Two of our four proposed pediatric hematology clinical sites (Boston Children's Hospital, Connecticut Children's Medical Center, Hasbro Children's Hospital (HCH) and Yale-New Haven Children's Hospital) will be randomized to implement WE CARE as standard of care for SCA patients. To assign the sites to either the control or the intervention group, we will first fix the number of sites to each group (i.e. 2 sites per group) and then assign sites to group using the random function for the uniform distribution in SAS 9.4.

***Study 3 (Aim 3): Qualitatively assess possible mechanisms linking SDoH interventions to improved health outcomes, such as increasing a parent's ability to manage their child's disease through medication adherence***

The Boston Medical Center-based team will conduct individual in-depth, semi-structured interviews with English- and Spanish-speaking parents of children aged  $\leq 12$  years who receive medical care for SCA at the two control sites (i.e., those in which the WE CARE intervention is not implemented).

## *Inclusion/Exclusion Criteria*

### ***Inclusion Criteria***

- Staff (e.g., physicians, nurses, front desk) at the outpatient hematology sites who are able to converse in English or Spanish, and are 18 years of age or older.
- English- or Spanish-speaking parents and caregivers of children with SCA aged 0-12 who receive care at one of the four study sites and take daily penicillin or hydroxyurea.

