### ***Exclusion Criteria***

- Staff at the four sites who are unable to converse in English or Spanish or are under 18 years of age.
- Parents  $< 18$  years of age, parents with children with SCA who are 13 years of age or older, parents whose child does not take daily penicillin or hydroxyurea, foster parents, caregivers who speak neither English nor Spanish, and caregivers previously enrolled in the study.

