### ***Definition of Primary and Secondary Outcomes/Endpoints***

Because qualitative research is by nature exploratory, we have not defined outcomes for the focus group discussions with practice staff (**Aim 1**); however, we will use the Promoting Action on Research Implementation in Health Services (PARIHS) framework to guide these discussions about facilitators and barriers to WE CARE implementation. Key areas of exploration will be (1) evidence: attitudes and beliefs about evidence of the WE CARE system; (2) context: organizational, systemic, and sociopolitical features that promote or hinder implementation of WE CARE; and (3) facilitation: attributes of the facilitation that supported or impeded the implementation, and needed adaptations.

Primary outcomes for **Aim 2** include the following:

- *Identification of unmet needs and provision of referrals.* Previously utilized forms will be used during baseline and follow-up questionnaires to measure whether practitioners provided families resource handouts.
- *Parental enrollment in community-based resources.* Baseline and follow-up questionnaires to measure enrollment in community resources.
- *Process measures.* Data will be collected on adherence to clinic visits (appointments kept, cancelled, and no-show). We will collect data on medications adherence in two ways. First, we will collect laboratory markers that are commonly affected by HU, including hemoglobin and hemoglobin F levels, white blood cell and absolute neutrophil counts, and MCV. We will also collect data on prescriptions written and filled for HU and penicillin through EHR review and parent report.
- *Health outcomes:* Data on vaso-occlusive episodes, acute chest syndrome and sepsis will be collected from the EHR at 6-month- and 12-month follow-up. Quality of life will also be assessed through both the PedsQL, which has been validated in children with sickle cell disease and is responsive to change, and the PedsQL Sickle Cell Disease Module.
- *Healthcare utilization outcomes:* Data on emergency department visits, hospitalizations, and clinic visits will be collected from the EHR at baseline and 12-month follow-up. We have chosen

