*\*Research Electronic Data Capture (REDCap) is a research focused, electronic web-based data capture system. REDCap is a data collection tool and allows for storage and management of both surveys and databases. REDCap is a secure storage system and meets HIPAA compliance standards. REDCap software will be used to facilitate parent consents, questionnaires, and forms.*

**Materials.** The research data will include questionnaires completed by parents/caregivers both in-person and via telephone, parent hair cortisol samples, and medical chart review. Only trained project staff at each clinical site will have access to participants' identifying information.

For the hair cortisol samples, we will be following the hair collection protocol developed by [name] from the University of Massachusetts (UMASS). Hair will be cut at the level of the scalp from 2-3 locations and cut to 3cm at the distal end. Hair samples will be placed directly into a plastic vial; each vial will be labeled by an ID number uniquely linked to each study subject (see below). Hair cortisol is stable at room temperature indefinitely, thus vials will be stored in a locked file cabinet.

For the *medical chart review*, existing trained research staff members at each study site, will collect the data. We decided to use existing research staff for the data collection component of the study since getting chart review credentialing is difficult at each of the study sites. At baseline and 12-month follow-up, medical charts will be reviewed in order to determine the number of appointments kept versus cancelled or no-show, the number of days covered by prescription refills for penicillin and hydroxyurea, and blood tests for monitoring hydroxyurea (including WBC, HB F%, and MCV). At 6-month and 12-month follow-up, medical charts will be reviewed in order to determine the frequency of vaso-occlusive episodes, acute chest syndrome, and sepsis diagnoses.

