## Statistical Power and Sample Considerations

We will enroll up to 235 subjects in this study, including up to 60 practice staff and 175 parents of children with SCA.

Because the goal for **Aim 1** is to examine the implementation of WE CARE in the outpatient pediatric hematology clinical setting our sampling will be purposeful. Based on our previous experience, we anticipate up to 15 practice staff per site will participate in focus group discussions.

For **Aim 2**, we are proposing to enroll 35 families from each of the four study sites (2 experimental, 2 control) to field test study logistics, including collecting empiric estimates of study parameters for a larger pragmatic trial. To demonstrate the feasibility of our study design, we use ED visits (primary

outcome) and penicillin adherence as examples. Assuming a 5% error rate, and based on our R00 WE CARE study, we expect a cluster coefficient no larger than 0.01. Based on recent data, we expect at least 80% of children in our control group to have at least one ED visit within our study observation period. We expect that our intervention group will have a much lower proportion, with ≤40% having with one or more ED visits. Our proposed study sample has >90% power to detect differences of at least 25% in the proportion of children with ED visits. In addition, based on estimates from the literature we expect a 9-month medication adherence of 40% and 10% in the intervention and control groups, respectively. Our study will have 90% power to detect differences of at least 20% in penicillin adherence, which is considered clinically significant. Consistent with CONSORT guidelines for pilot studies, we will not use results from this study to determine efficacy, since effects sizes from pilot studies likely overestimate or underestimate the true effect size; rather we will determine empiric estimates from the control group as the basis for power calculations for a future multi-site trial.

For **Aim 3**, in order to explore an array of beliefs and practices regarding family contextual factors that promote or prevent effective SCA management, enrollment will continue until saturation is reached (i.e. more interviews will not generate additional information) in primary research questions. Based on our previous experience, we expect 25-35 parents will be sufficient to reach saturation.

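### The 90% power stated for penicillin adherence assumes all 140 children are evaluable, but eligibility on either penicillin or hydroxyurea does not guarantee that

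*Combined protocol and SAP*

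**What the plan says.** The Inclusion Criteria admit parents of children "aged 0-12 who receive care at one of the four study sites and take daily penicillin or hydroxyurea". The Exclusion Criteria mirror this and remove "parents whose child does not take daily penicillin or hydroxyurea", so a child on one of the two drugs qualifies.

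Background and Significance, in the paragraph on children with sickle cell anemia, states that "Use of daily antibiotic prophylaxis in children with SCA until age 5 years reduces mortality" and that guidelines recommend "hydroxyurea (HU) be offered to children with SCA beginning at 9 months of age".

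Two adherence measures are planned. Under Definition of Primary and Secondary Outcomes/Endpoints, "we will collect laboratory markers that are commonly affected by HU", and data are also collected on prescriptions written and filled for both drugs. Under Data Collection Methods, the chart review records "the number of days covered by prescription refills for penicillin and hydroxyurea".

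Statistical Power and Sample Considerations plans 35 families at each of four sites, a 5% error rate and a cluster coefficient of at most 0.01. It expects adherence of 40% in the intervention group and 10% in the control group, and concludes: "Our study will have 90% power to detect differences of at least 20% in penicillin adherence". It gives no expected number of children on each drug.

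**The concern.** The power statement is made for the study as a whole, and the only Aim 2 sample is 4 × 35 = 140 families. The eligibility rule does not make penicillin adherence measurable in all of them. On the protocol's own description, a child past age 5 may enter on hydroxyurea alone, and an infant under 9 months on penicillin alone. The number contributing to the penicillin comparison is therefore some unknown part of 140.

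Two things are at stake. The stated power describes a sample the trial may not have. In addition, the protocol says control-group estimates will be the basis for sizing the future trial, and a control-group penicillin estimate from fewer children is less precise than the plan implies. The Aim 2 analysis text also does not say how a child not prescribed a drug is handled in that drug's measure.

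**Working it through.** **Inputs from the power section.** 35 families per site, two sites per arm, so 70 per arm; 5% error rate, sidedness not stated; cluster coefficient 0.01; expected adherence 10% control and 40% intervention; smallest difference 20 points. I read the last as 10% versus 30%.

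**Assumption.** f is the share of enrolled children prescribed penicillin, taken as equal across sites. The documents do not give it, so a range is shown.

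**Formulas.**
- Children per arm: n = 70f.
- Design effect: 1 + (35f − 1) × 0.01. Effective number per arm: n_eff = n / design effect.
- Power, pooled null variance: Φ{[d − z·√(2p̄(1−p̄)/n)] / √([p₁(1−p₁) + p₂(1−p₂)]/n)}, with z = 1.96 two-sided, p̄ the mean of p₁ and p₂, and n_eff in place of n when clustering is applied.

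**Attempt to reproduce the stated 90% with all 140 children, 10% versus 30%.**
- Two-sided, no clustering, n = 70: (0.20 − 1.96√(0.32/70)) / √(0.30/70) = (0.200 − 0.1325)/0.0655 = 1.03, power 85%.
- Two-sided with the coefficient, design effect 1.34, n_eff = 52.2: (0.200 − 0.1534)/0.0758 = 0.615, power 73%.
- One-sided: 91% without clustering, 83% with the coefficient.
- Measured down from the intervention rate instead (20% versus 40%), two-sided with the coefficient: 61%.

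At 10% versus 30%, no variant using the stated coefficient comes within 2 points of 90%; unpooled, arcsine and continuity-corrected two-sided versions give 75%, 75% and 64%. The pooled one-sided test without clustering does reach it. That test needs 67 per arm, and 67/70 = 96% of children on penicillin.

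**Effect of the share on penicillin.** The 38% row is 5/13: ages spread evenly over 13 one-year bands, with penicillin used only under 5.

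| Share f | Children (total) | n_eff per arm | 10% v 30%, two-sided, no clustering | 10% v 30%, two-sided, coefficient 0.01 | 10% v 30%, one-sided, no clustering | 10% v 40%, two-sided, coefficient 0.01 |
|---|---|---|---|---|---|---|
| 100% | 140 | 52.2 | 85% | 73% | 91% | 95% |
| 75% | 105 | 41.9 | 73% | 63% | 83% | 90% |
| 50% | 70 | 30.0 | 55% | 49% | 68% | 78% |
| 38% | 54 | 23.9 | 45% | 41% | 58% | 68% |

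The normal approximation makes no allowance for having only two sites per arm, so these figures are, if anything, favourable to the plan.

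**Precision of the control-group estimate at 10% adherence, no clustering.** The 95% half-width is 1.96√(0.09/70) = 7 points with 70 children and 1.96√(0.09/27) = 11 points with 27.

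**The case against.** The strongest reply has four parts.

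First, age 5 is background text and not a study rule. Older children may still take penicillin and a child may take both drugs, so the share could be high. The 38% figure also sits at the low end of its own premise. If penicillin is used only under 5, a child aged 5 to 12 not on hydroxyurea is ineligible. With hydroxyurea use u at those ages, even clinic ages and all under-5s on penicillin, the share is 5/(5 + 8u): 38% at u = 100%, 56% at 50% and 71% at 25%. This stands, and it is why a range is given and no single share is claimed.

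Second, part of the gap comes from the power calculation itself: at the full 140 the two-sided figure is already 85% without clustering and 73% with it. This also stands. A reader might take the loss from eligibility to be 90% to 41%. With the coefficient applied, it is 73% to 63%, 49% or 41%, depending on the share. At the expected 10% versus 40%, power holds at 90% down to a share of 75%.

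Third, a reader might infer that children never prescribed a drug will be scored as non-adherent, or that the control-group estimate is distorted whichever way they are handled. The documents support neither. Nothing says such children will be scored as non-adherent; written prescriptions are to be collected and can supply the denominator and any end date. The chart-review text presents the blood tests as hydroxyurea monitoring. Counting only children prescribed the drug costs precision and does not in itself add bias. What remains is that the scoring rule is not written down.

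Fourth, penicillin adherence is one of two illustrative examples, ED visits are named as the primary outcome, and the pilot is not to be used to judge efficacy. This limits the consequence but does not make the stated figure correct.

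**Conclusion.** The point holds for the power statement. The claimed 90% for a 20-point difference in penicillin adherence is not delivered under a two-sided 5% test at any share of children on penicillin. With the stated coefficient, power is 73% at best and falls to 49% if half are on penicillin. The shortfall at the full 140 is a separate problem, which the eligibility rule makes worse. Only a one-sided test without clustering meets the claim, and only if about 96% of children are on penicillin.

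The conclusion that the figure needs restating rests on the eligibility text and the plan's own inputs. The size of the eligibility effect depends on the unknown share. The missing per-drug denominator is a gap in wording and is not evidence that the estimates will be biased.

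**What to change.** In Statistical Power and Sample Considerations, restate the penicillin power for the expected number of children prescribed penicillin, apply the 0.01 coefficient and state whether the test is one- or two-sided. Alternatively, replace the example with adherence to the child's prescribed drug or drugs, which every eligible child has.

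As supporting wording in the endpoint and Aim 2 analysis sections, use the planned prescriptions-written data to compute adherence to each drug among children prescribed it, up to any documented stop. Report the number evaluable per arm and site.

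The cost is a less favourable stated power and a few sentences of protocol text. Eligibility, sample size and the ED-visit outcome are unchanged.
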